### 7.3. Missing Data

Missing data (missing, incomplete or partial dates, AE measurement [including missing AE severity and relationship], prior and concomitant medications and death date) will be handled as per [0](#) of this SAP.

Missing immunogenicity data will not be imputed. Titers below assay cut-off (i.e., lower limit of quantification or  $<$  LLOQ) will be replaced by half the assay cut-off (LLOQ/2) and titers above the assay cut-off (i.e., upper limit of quantification or  $>$  ULOQ) will be replaced by the ULOQ for the purpose of GMC/GMT computation.

[figure not shown]
### 7.4. Multiple Comparisons / Multiplicity

There are 3 primary endpoints to be accounted for in this study. In order to eliminate the need to adjust alpha, testing for these endpoints will take the following sequence:

First sequence:

- The upper limit (UL) of the 2-sided 95% CI of the GMC ratio between the Control group (at Day 91) versus Co-Ad group (at Day 91) for anti-gE Ab 1-month after the second HZ/su vaccine dose is  $\leq 1.5$ .

CCI

AND

- The UL of the 2 sided 95% CI of the GMT ratio (control group divided by Co-Ad group) between the control group versus Co-Ad group for RSV-A neutralizing titer one month after the RSVPreF3 OA investigational vaccine dose is  $\leq 1.5$ .

Second sequence:

- The UL of the 2 sided 95% CI of the GMT ratio (control group divided by Co-Ad group) between the control group versus Co-Ad group for RSV-B neutralizing titer one-month after the RSVPreF3 OA investigational vaccine dose is  $\leq 1.5$ .

Testing will progress in the 2nd sequence only if the 1st sequence is a success.

## 7.5. Examination of Subgroups

Subgroup analyses by age category (50-59 YOA, 60-69 YOA,  $\geq 70$  YOA) will be performed for demography summaries based on ES and PPS. Subgroup analyses by age category, race, ethnicity and gender will be performed for secondary immunogenicity endpoints (anti-gE antibody concentrations, RSV-A and RSV-B titers only), solicited events within 7 days, unsolicited events and grade 3 unsolicited events within 30 days of each dose, serious AEs and pIMD up to study end (6 months after last dose) summaries.

## 8. OUTPUT PRESENTATIONS

[figure not shown]
[APPENDIX 1](#) shows conventions for presentation of data in outputs.

The templates provided with this SAP describe the presentations for this study and therefore the format and content of the summary tables, figures, and listings to be provided by IQVIA Biostatistics. Statistical output numbering will follow 'ICH E3 Structure and Content of Clinical Study Reports'.

## 9. DISPOSITION AND WITHDRAWALS

All participants who are enrolled in the study will be accounted for in this study.

CCI

## 9.1. Disposition

Participant disposition for all analysis sets and both Per-protocol sets, withdrawals, and reasons for exclusion from each analysis set, including inclusion as well as exclusion criteria will be presented for the SCR, ENR and ES. Specifically, the number of participants, vaccinated, completed the study, discontinued from the study and the reason for discontinuation will be summarized by study intervention group and overall for the ES. Additionally, the number of participants returning for each visit for the ES will be presented.

## 9.2. Protocol Deviations

Protocol deviations (PDs) will be collected in a PD log, as detailed in the PDMP. All PDs will be assessed as either important or non-important. PDs will be reviewed by the sponsor, and their status confirmed by the time that all data are cleaned for the First and EOS Analyses. A summary table presenting the number and percentage of participants with important PDs and most importantly those associated to elimination from PPS and the number and percentage of participants excluded from the PPS analyses will be presented for participants in the SCR by study intervention group and overall. A listing of all PDs including an indicator of those excluded from the PPS and an indicator of COVID-19 causality will be provided.

# 10. DEMOGRAPHIC AND OTHER BASELINE CHARACTERISTICS

Demographic data and other baseline characteristics will be presented for the ES and PPS by group and overall. The following demographic and other baseline characteristics will be reported for this study:

- Age (years) – at the time of first study intervention
- Age category (50-59, 60-69,  $\geq 70$ ,  $\geq 75$  YOA)
- Sex
- Race (as per Clinical Data Interchange Standards Consortium [CDISC] categories)
- Ethnicity
- Country
- Center

For web posting purposes, the demographic characteristics will be presented for the enrolled set. In addition, the following age categories will be summarized: 18-64, 65-84, and  $\geq 85$ . If the summary of demographics meets the

CCI

criteria for de-identification, as described in the relevant procedural document, a de-identified version will be produced.

No statistical testing will be carried out for demographic or other baseline characteristics.

## **11. GENERAL MEDICAL / VACCINATION HISTORY AND EXAMINATIONS**

Information both on Medical / Vaccination History will be summarized for the ES by group and will be reported, along with pregnancies, as tabular listing based on SCR respectively.

- Medical History will be coded using Medical Dictionary for Regulatory Activities (MedDRA) central coding dictionary, Version 25.1 or higher.
- Data captured on the “Medical History” page of the eCRF will be presented by MedDRA System Organ Class (SOC), High Level Terms (HLT) and Preferred Term (PT). Medical occurrences that begin before the start of study intervention but after obtaining informed consent will be recorded on the Medical History section of the eCRF, not the AE section.

A listing of medical / vaccination history data will be provided.

## **12. PRIOR, CONCOMITANT AND CO-ADMINISTERED VACCINATIONS**

[figure not shown]
Prior, concomitant and co-administered vaccination will be coded with the current version of the World Health Organization Drug Dictionary (WHODD).

Prior vaccinations are vaccinations per protocol given to participants prior to the dosing of study intervention and are recorded on the eCRF.

Concomitant vaccinations are defined as any vaccine that the participant is receiving as of the time of enrolment or receives during the study (other than study interventions) as recorded on the “Concomitant Vaccination” page of the eCRF.

The number and percentage of participants and doses with concomitant vaccination during the 30-day follow-up period (i.e., on the day of vaccination and 29 subsequent days) will be summarized by group after each vaccine dose

CCI

and overall, with exact 95% CIs.

## 13. MEDICATIONS

The number and percentage of participants and doses using concomitant medication (any medication, any medical device, any antipyretic and any antipyretic taken prophylactically, respectively) during the 7-day follow-up period (i.e., on the day of last study intervention and 6 subsequent days) and during the 30-day follow-up period (i.e., on the day of last study intervention and 29 subsequent days), will be summarized by study intervention group for each study intervention administration and overall with exact 95% CIs for the ES. Concomitant medications will also be presented in listings.

See [APPENDIX 2](#) for handling of partial dates for medications, in the case where it is not possible to define a medication as prior or concomitant, the medication will be classified by the worst case, i.e., concomitant.

- ‘Prior’ medications are medications which started prior to the dose of study intervention.
- ‘Concomitant’ medications are medications which started on or after the day of the administration of study intervention.

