## **6.7 Concomitant Therapy**

At each study visit/contact, the investigator or his/her delegate should question the participant and/or the participant's caregiver about all medications/products taken, and vaccinations received by the participant.

The following concomitant medication(s)/product(s)/vaccine(s) must be recorded in the eCRF:

- All concomitant medications ongoing at screening, and all concomitant medications including vaccines, administered after the first dose of study intervention (Visit 1 [Day 1] to EoS), except vitamins and dietary supplements.
- All concomitant medications leading to discontinuation of the study intervention or elimination from the analysis, including products/vaccines (Refer to [Section 5.2.2](#) and [Section 9.2.1](#)).
- All concomitant medication which may explain/cause/be used to treat an SAE/pIMD including vaccines/products, as defined in [Sections 8.3.1](#) and [10.3.6](#). These must also be recorded in the Expedited Adverse Event report.

- Any prophylactic medication (e.g., analgesics, antipyretics) administered on the day of study vaccination in the absence of any symptom and in anticipation of a reaction to the vaccination.

The medical monitor should be contacted if there are any questions regarding concomitant or prior therapy.

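### SAP 13 sorts medications by start date alone, so drugs begun before a dose and still being taken drop out of the 7-day and 30-day concomitant-use tables

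*SAP*

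**What the plan says.** SAP 13 (Medications) sets out what will be tabulated: "The number and percentage of participants and doses using concomitant medication", with rows for any medication, any medical device, any antipyretic and any antipyretic taken prophylactically. The tables are for the Exposed Set, by study group, for each administration and overall. The windows are given as "on the day of last study intervention and 6 subsequent days" and "on the day of last study intervention and 29 subsequent days".

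The same section then gives two definitions. The concomitant class is made up of "medications which started on or after the day of the administration of study intervention". A drug begun before the dose is prior, with no exception for one that is still being taken. Where a partial date makes the choice impossible, "the medication will be classified by the worst case, i.e., concomitant".

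Two other places use the word more widely:

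- Protocol 6.7 (Concomitant Therapy) requires the eCRF to hold "All concomitant medications ongoing at screening, and all concomitant medications including vaccines, administered after the first dose of study intervention".
- SAP 12, on vaccinations, counts as concomitant "any vaccine that the participant is receiving as of the time of enrolment or receives during the study".

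SAP 3.3 states that there are no changes to the analyses defined in the protocol.

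**The concern.** The tables are described as medication use during a period, but the definition beneath them measures medication starts. A participant who takes a drug every day of the window is not counted if the first tablet came before the dose. SAP 13 plans no summary of prior medications, so this use appears in no Section 13 summary table.

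The situation will be common. Protocol 5.1 admits participants aged 50 and over with stable chronic conditions under treatment, and names diabetes, hypertension and cardiac disease.

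The antipyretic row matters most to a reader. It gives context for the fever and pain results, and Protocol 5.6 itself treats recent antipyretic or analgesic use as a possible reason to postpone a dose. If regular users are missing from that row, the context is incomplete.

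**Working it through.** The plan states no figure for medication use, so there is nothing to reproduce. The check compares the SAP 13 rule with the wider scope (ongoing at the dose, or given after it) for each possible timing of a drug.

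| Timing of the drug | SAP 13 class | Counted under SAP 13 | Counted if use in the window is the test |
|---|---|---|---|
| Started and stopped before the dose | Prior | No | No |
| Started before the dose, taken during the window | Prior | **No** | **Yes** |
| Started on the dosing day before the injection, taken that day | Meets both definitions | Unclear | Yes |
| Started on the dosing day after the injection, or later in the window | Concomitant | Yes | Yes |

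The second row is the loss. The worst-case rule does not recover it, because that rule applies only when a drug cannot be classified. A drug with a known earlier start date can be classified, as prior. The third row shows that the two definitions also overlap, since one refers to the dose and the other to the day of administration.

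**Anchor dose.** The definitions speak of a single dose, the windows refer to the last study intervention, and the tables are for each administration. Take a drug started on Day 10 and continued past Day 91, and look at the 30-day tables.

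- Anchor is the first dose: the drug is concomitant throughout and counts at every dosing visit in both groups.
- Anchor is each dose: in the Control group (dosing on Days 1, 31 and 61) it counts at Day 1 and is lost at Days 31 and 61. In the Co-Ad group (dosing on Days 1 and 61) it counts at Day 1 and is lost at Day 61.

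On the per-dose reading the loss is two of three dosing visits in one group and one of two in the other, so the overall figures could differ between groups for a purely definitional reason. The SAP does not say which reading applies. A drug started before dose 1 is lost on either reading.

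**Size, as an assumption only.** The shortfall in a row equals the share of participants whose only use in the window is of drugs started earlier. With 265 planned per group:

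- Any medication, assumed share 20% to 70%: 0.20 × 265 = 53 and 0.70 × 265 = 185.5, so about 53 to 186 participants per group.
- Any antipyretic, assumed share of regular users 5% to 10%: 0.05 × 265 = 13.25 and 0.10 × 265 = 26.5, so at most about 13 to 27 per group. This is a ceiling: it ignores the Protocol 5.6 delay criterion and supposes that no regular user also starts a new antipyretic in the window.

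**Reach.** The definition feeds the descriptive Exposed Set tables. The per-protocol sets exclude participants for prohibited concomitant medication, but that is decided through Protocol 5.2.2 and 9.2.1 and the deviation review in SAP 5.1, without reference to the SAP 13 classes. The ANCOVA models and success criteria do not use medication data.

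**The case against.** **Protocol 6.7 is a recording rule.** It specifies no table, and Protocol 9.3 leaves safety summaries to the SAP. This stands. A reader might infer that the SAP departs from an analysis the protocol defined; the documents do not support that. The inconsistency is over which drugs are called concomitant.

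**Antipyretics are partly covered.** Protocol 5.6 lists antipyretic or analgesic use in the 3 days before dosing among the reasons for which a dose may be postponed, and the delay criteria are checked before every dose in both groups. Antipyretics started on the dosing day, including prophylactic ones taken after the injection, still count. This stands as a reduction. Postponement is discretionary, so some regular users could still be dosed and then missed by the table.

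**The drugs are not lost from the report.** It is tempting to say that regular use would be reported as no use. SAP 6 requires all collected data to be listed unless otherwise specified, and drugs ongoing at screening are collected, so they should appear in listings. SAP 13 itself mentions listings only for concomitant medications, so this rests on the general rule.

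**No safety comparison is biased.** A reader might infer that the definition distorts the reactogenicity comparison. SAP 16 plans no statistical comparison of safety between groups, solicited events come from the eDiary, and nothing in the plan adjusts or excludes them using the medication tables. Any masking by a long-term drug would occur however it was tabulated.

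**Counting only new starts can be a sensible choice.** Chronic therapy could swamp an any-medication row. But SAP 13 does not state that purpose, and its tables are described as use.

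**The SAP 12 parallel is weak,** because a vaccination is a single event. This is fair, and the point does not depend on it.

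**Conclusion.** The point holds as a minor error of definition. As written, SAP 13 leaves drugs started before dosing and still taken out of tables that claim to show use during the 7-day and 30-day windows, and it leaves the anchor dose open. The tables would understate use in the window. The documents give no medication rates, so the amount cannot be derived from them; the counts above only illustrate assumed shares.

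The further loss at later doses is conditional on reading the definitions per dose and should not be stated as fact. The effect is confined to descriptive Exposed Set medication tables. The output templates that accompany the SAP are not in the documents reviewed and could show a different intention, but the SAP text should be sufficient without them.

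**What to change.** In SAP 13, replace the two definitions and state that they apply separately to each dose, with that dose as the anchor:

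- Concomitant: any medication whose use overlaps the window, that is, started on or before the last day of the window and either ongoing or ended on or after the dose date.
- Prior: stopped before the dose date.

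Align the window wording with the same anchor. Within each table, show medications ongoing at vaccination separately from those newly started, antipyretics included. This keeps the new-start count for readers who want it and removes the double classification of drugs begun on the dosing day.

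The cost is a few lines of SAP text, a changed derivation and extra table rows. No new data are needed: Protocol 6.7 already has ongoing drugs recorded, and SAP Appendix 2 already provides for incomplete medication start and end dates.

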## 14. STUDY INTERVENTION EXPOSURE

Exposure to study intervention will be presented for the ES per study intervention group and overall. The date and time of study intervention administration will be taken from the eCRF “Study intervention administration” forms (separate forms for HZ/su and RSVPreF3 OA investigational vaccine). For dosing instructions and route, refer to Table 8 of the Protocol.

## 15. IMMUNOGENICITY OUTCOMES

The primary analysis will be based on the applicable PPS (i.e., RSV PPS or HZ/su PPS) for analysis of immunogenicity. If, in any study intervention group, the percentage of vaccinated participants with serological results excluded from the applicable PPS for analysis of immunogenicity is 5% or more, a second analysis based on the ES will be performed to complement the PPS analysis.

CCI

## 15.1. Primary Immunogenicity

### 15.1.1. Primary Immunogenicity Variables & Derivations

The primary immunogenicity endpoints are:

- Anti-gE ELISA Ab concentrations (mIU/mL) expressed as between groups GMC ratio, 1-month after the second HZ/su dose (Day 91 for both Co-Ad group and Control group)
- RSV-A neutralizing titers (ED60) expressed as between groups GMT (ED60) ratio, 1 month after the RSVPreF3 OA investigational vaccine dose (Day 31 for Co-Ad group and at Day 61 for Control group)
- RSV-B neutralizing titers (ED60) expressed as between groups GMT (ED60), 1-month after the RSVPreF3 OA investigational vaccine dose (Day 31 for Co-Ad group and Day 61 for Control group)

See [7.4](#) for details on the handling of multiple primary endpoints.

### 15.1.2. Intercurrent Event Handling and Data Imputation for Primary Immunogenicity Variables

Missing data will not be replaced.

### 15.1.3. Primary Analysis of Primary Immunogenicity Variables

The primary immunogenicity endpoints will be analyzed as follows:

- Between groups GMC ratio for HZ/su vaccine between the Control group over Co-Ad group for gE Ab concentrations (IU/mL) at 1-month after the second HZ/su vaccination (i.e., at Day 91 for both Co-Ad and Control groups) and 2-sided 95% CI will be computed.
  - The least square point estimate and its 95% 2-sided CIs of the between group GMC ratio will be derived from an ANCOVA model on log10 transformed concentrations and presented alongside descriptive GMCs and 95% CIs. The ANCOVA model will include the treatment group and age category (age at vaccination: 50 to 69, 60 to 69, or  $\geq 70$  YOA) as fixed effects, and the pre-vaccination log10-transformed concentration as covariate. The results will be presented in tables as well as graphs using forest plots.
- Between group GMT ratio for RSV investigational vaccine between the Control group over Co-Ad group

CCI

for RSV-A neutralizing titers (ED60) at 1-month after the RSVPreF3 OA investigational vaccine dose (i.e., at Day 31 for Co-Ad group, and at Day 61 for Control group) and 2-sided 95% CI will be computed.

- The least square point estimate and its 95% 2-sided CIs will be derived from an ANCOVA model on log10 transformed titers and presented alongside descriptive GMTs and 95% CIs. The same ANCOVA model used for the HZ/su GMC ratio will be applied for this summary. The results will be presented in tables as well as graphs using forest plots.
- Between group GMT ratio for RSV investigational vaccine between the Control group over Co-Ad group for RSV-B neutralizing titers (ED60) at 1-month after the RSVPreF3 OA investigational vaccine dose (i.e., at Day 31 for Co-Ad group, and at Day 61 for Control group) and 2-sided 95% CI will be computed.
  - The least square point estimate and its 95% 2-sided CIs will be derived from an ANCOVA model on log10 transformed titers and presented alongside descriptive GMTs and 95% CIs. The same ANCOVA model used for the HZ/su GMC ratio will be applied for this summary. The results will be presented in tables as well as graphs using forest plots.

A successful primary immunogenicity conclusion will require:

First sequence:

- The upper limit of the 2 sided 95% CI of the GMC ratio between the Control group (at Day 91) versus Co-ad group (at Day 91) for anti-gE Ab 1-month after the second HZ/su vaccine dose is  $\leq 1.5$ .

AND

- The upper limit of the 2 sided 95% CI of the GMT ratio between the Control group (at Day 61) versus Co-ad group (at Day 31) for RSV-A neutralizing titer 1-month after the RSVPreF3 OA investigational vaccine dose is  $\leq 1.5$ .

Second sequence:

- The upper limit of the 2 sided 95% CI of the GMT ratio between the Control group (at Day 61) versus Co-ad group (at Day 31) for RSV-B neutralizing titer 1-month after the RSVPreF3 OA investigational vaccine dose is  $\leq 1.5$ .

Testing will progress in the second sequence only if the first sequence is a success, so that no further adjustment of alpha is required.

Note: For anti-gE antibody concentration summaries, pre-vaccination is at Visit 1 for Co-Ad group and for Control

CCI

Group. For RSV-A and RSV-B neutralizing titer and concentration summaries, pre-vaccination is at Visit 1 for Co-Ad group and at Visit 2 for Control group.

#### **15.1.4. Analysis for Primary Immunogenicity Variables**

Sensitivity analysis will be performed on the primary immunogenicity endpoints using the same primary ANCOVA model with the treatment group and age category (age at vaccination: 50-59, 60-69 or  $\geq 70$  years) as fixed effects and the pre-vaccination log10-transformed concentration or titer as applicable, as regressors, and with the addition of center as a random effect.

A second sensitivity analysis for the primary immunogenicity endpoints for RSV-A/B will be performed as described in Section 15.1.3. on a modified PPS including participants who received only one dose of HZ/su vaccine in the Co-Ad group.

### **15.2. Secondary Immunogenicity**

[figure not shown]
The primary analysis of secondary immunogenicity endpoints will be based on the applicable PPS (i.e., RSV PPS or HZ/su PPS) for analysis of immunogenicity. If, in any vaccine group, the percentage of vaccinated participants with serological results excluded from the PPS for analysis of immunogenicity is 5% or more, a second analysis based on the ES will be performed to complement the PPS analysis.

